## REVISION HISTORY

Version	Date	Significant Revisions
1.0	08 August 2022	Initial Version
2.0	06 October 2022	Updated miscellaneous language and included language to exclude women with positive pregnancy test at any visit.

## Protocol Synopsis

Study Title: A Prospective, Non-Randomized, Multi-Center Observational Study to Establish a Physical Baseline Profile for Individual Study Subjects Using Various Modalities and Identify Deviations via Longitudinal Monitoring that May Develop Over Time and May be Relevant to Human Health and Longevity.	
Short Title	PUER Research Clinical Study
Study Type	This is a minimal-risk, prospective, non-randomized, multi-center population based observational study to establish a physical baseline profile for individual study subjects using various modalities and identify deviations through longitudinal monitoring that may develop over time and may be relevant to human health and healthy longevity.
Study Description	
The three key elements of the Puer Research protocol include (1) Medical history and physical exam (PE), (2) molecular and laboratory profiling and (3) non-invasive imaging and wearables/ “quantified self” measurements. The medical history and PE will consist of a comprehensive medical history and physical examination, administered by a trained Research Associate. Laboratory assessments will be conducted using peripheral blood samples, and potentially urine, stool or saliva samples. Non-invasive imaging assessment will consist of magnetic resonance imaging (MRI) and computerized tomography (CT) scans. Other functional assessments, including respiratory, cardiac and other functions, as well as self-quantifiable assessments via wearables will also be conducted.
 
The study will result in longitudinal real world data collection to inform if any modalities employed here can inform of baseline deviations for individuals. Researchers at study sites will not be blinded to the data being collected during this study.

Study Sites	This study will be conducted in up to 20 study sites in the United States.
Study Population	The study will be conducted in up to 10,000 participants.
Study Duration	72 months
Enrollment Duration	36 months
Objectives	

• The primary objective is to establish a baseline profile for individual healthy study subjects using various modalities and monitor them longitudinally to identify deviations that develop over time and may be relevant to human health and longevity. The secondary objective is to identify the modality that has the highest impact on the identification of deviations from baseline profile.

Adverse Event (AE) Monitoring	Adverse events associated with the study procedures, of venipuncture, non-invasive imaging and functional tests will be reported, although they are expected to be limited due to the nature of these common procedures.

Inclusion Criteria	To participate in the study, patients must meet the following criteria;						
	
 
1. Male or non-pregnant female; age 18 to 90.
 
2. Absence or presence of any medical history or any signs or symptoms of any disease.
 
3. Women of childbearing potential (WOCBP) must have a negative urine pregnancy test (UPT) at all visits.
 
						
Exclusion Criteria	Patients who meet any of the following criteria will be excluded from study participation;						
	
 
1. Unwillingness or inability to participate in the study
 
2. Unwillingness or inability to provide written Informed Consent Form
 
3. WOCBP with positive pregnancy test at enrollment or at any visit
 
						
Study Schedule	Event	Baseline Visit	6-Month Visit $\pm$ 1month	12-Month Visit $\pm$ 1month	18-Month Visit $\pm$ 1month	24-Month Visit $\pm$ 1month	36-Month Visit $\pm$ 1month
	Informed Consent	X					
	Review of Inclusion/Exclusion Criteria	X					
	Medical history and physical exam	X	X	X	X	X	X
	UPT for WOCBP	X	X	X	X	X	X
	Whole Genome Sequencing Analysis	X					
	Biochemical/Omics Analysis	X	X	X	X	X	X
	Non-Invasive Imaging	X	X	X	X	X	X
	Functional Assessments (as needed)		X	X	X	X	X
	Wearables and Quantified Self Assessments (as needed)		X	X	X	X	X
	Adverse Event Monitoring	X	X	X	X	X	X

1. UPTs must have a minimum sensitivity of 25 mIU  $\beta$ -hCG/mL.
2. WOCBP include any female who has experienced menarche or is 10 years of age or older and who has not undergone successful surgical sterilization (hysterectomy, bilateral tubal ligation, or bilateral oophorectomy) or is not postmenopausal (defined as amenorrhea  $>12$  consecutive months in women 50 years of age and older).
3. See Section 3.3.2 for detailed schedule of imaging

## ABBREVIATIONS

AE	Adverse Event
CFR	Code of Federal Regulations
CRF	Case Report Form
CT	Computed Tomography
DNA	Deoxyribonucleic Acid
ECG	Electrocardiogram
EDC	Electronic Data Capture
EEG	Electroencephalogram
EMG	Electromyography
FDA	Food and Drug Administration
GBCM	Gadolinium-Based Contrast Media
GCP	Good Clinical Practice
GINA	Genetic Information Nondiscrimination Act
HR	Heart Rate
HRV	Heart Rate Variability
IRB	Institutional Review Board
miR	Micro-RNA
mL	Milliliter
mRNA	Messenger RNA
MRI	Magnetic Resonance Imaging
NNT	Number Needed to Treat
PE	Physical Examination
PHI	Protected Health Information
PMI	Precision Medicine Initiative
RNA	Ribonucleic Acid
SAE	Serious Adverse Event
UPT	Urine Pregnancy Test
US	United States
WGS	Whole Genome Sequencing
WOCBP	Women of Childbearing Potential

## 1. Introduction

### 1.1. Background

Scientific and medical progress has been exponential over the past decades, yet the implementation of new technologies into every-day clinical practice can lag by 5-10 years, thus preventing a large portion of the population from benefiting from those advances during their meaningful lifetime (Glasziou & Haynes, 2005). Earlier detection leads to earlier intervention where needed and accordingly, deploying novel technologies is the cornerstone of avoiding undesirable outcomes. However, the path and timeline of discovery, development, regulatory approval, and commercialization can delay implementation of potentially life-saving technologies by 5-10 years.

There have been tremendous advances in the understanding of health, and longevity over the past decades. The early 2000s marked the ushering in of the genomic era, with the sequencing of the human genome (Guttmacher & Collins, 2003). Since that time, the required time and cost of genome sequencing has dropped dramatically, and the actionability of sequencing the entire human genome has increased exponentially (Hayden, 2014) (Scaria, 2014) (Dorschner, et al., 2013) (Amendola, et al., 2015) (Goldstein, 2013) (Bromberg, 2013). Beyond DNA sequencing, other “omics” analyses such as DNA methylation, RNA sequencing, proteomics, metabolomics and lipidomics technologies have matured to the point of significant reproducibility, providing important biological insights. Conventional biochemical laboratory technologies have improved and matured and there are a large number of diagnostics laboratory tests available in the commercial setting.

Similarly, non-invasive imaging techniques, such as magnetic resonance imaging (MRI) and computed tomography (CT) modalities have continued to evolve, using artificial intelligence- and computer-aided design-based analytical methods to improve the quality of diagnostic images and enhance clinical care (Uppot, et al., 2018) (Onal, et al., 2014) (Zhu, et al., 2018) (Anthimopoulos, et al., 2016) (Li, et al., 2008) (Arnoldi, et al., 2010) (Lemaitre, et al., 2015) (Yang, et al., 2014)

The above techniques, as well as others, can now be applied both in healthy individuals, as well as in individuals exhibiting certain deviations from a healthy baseline profile. However, the impact of deploying a large suite of genomic, biochemical, and non-invasive imaging modalities on human health and longevity is unknown. Understanding such impact of the combination of such modalities, as well as the relative contribution of individual modalities, represents a leap forward in the understanding of human health and healthy longevity.

### 1.2. Rationale

The fundamental basis of the Puer (“Previously Unrecognized Evidence of Risk”) study is based in the central dogma of biology (Crick, 1970). The central dogma of biology stipulates that human health and longevity are determined in the context of the interactions of the human genome (DNA) and the environment, and these interactions will determine the transcription of DNA to RNA, the translation of RNA to proteins, and such structural and functional proteins will determine the complex molecular milieu in an individual, leading to quantifiable phenotypes of health and disease. The human genome (DNA) contains approximately 6.4 billion nucleotides organized into ~25,000 genes, transcribed into approximately 100,000 different RNA transcripts and ~25,000-28,000 transcribed gene constructs that are translated into about 20,000 human proteins. These proteins make up human cells and organs and

regulate the intracellular and extracellular milieu of the human body, containing over 10,000 small molecules and lipid/phospholipid species.

Technologies exist today to measure the majority of these biochemical and “omics” components. Whole genome sequencing (WGS) technologies are now able to decipher all 6.4 billion nucleotides in each individual (“wet lab component”), and cutting-edge bioinformatics pipelines can tie individual genetic variants to disease susceptibility, pharmacogenomics, and disease carrier status (“dry lab component”) (Netto & Kaul, 2019). Both messenger RNA (mRNA) and micro-RNA (miR) can be sequenced from blood-based, peripheral circulating cells and such gene expression signatures have already been translated to clinically approved diagnostic blood tests (Rosenberg, et al., 2010). A number of different techniques are available for proteomics profiling based on mass spectrometry (Han, et al., 2008) and other techniques, such as aptamers, somamers (Gold, 2010) and dual-antibody approaches (Assarsson, et al., 2014). Such proteomics signatures have also been turned into diagnostic signatures (Ganz, et al., 2016). Metabolomics profiling is now also a reality, using mass spectrometry (Yet, et al., 2016), NMR-technologies (Fest, et al., 2019) and other techniques (Bennuru, et al., 2017). Similar to metabolomics, lipidomics profiling is also available today (David, et al., 2022). Many commercial laboratories have developed Food and Drug Administration (FDA)-cleared diagnostic and screening tests that can be applied in everyday clinical practice.

While non-invasive imaging modalities, such as CT and MRI have been around for several decades, artificial intelligence-based post-processing and interpretation approaches are transforming the imaging field with the potential to radically impact clinical care (Uppot, et al., 2018).

Yet another important concept is the concept of the “N-of-1” clinical study (Schork, 2015). The traditional path in science and medicine has been a population-based approach, where large populations were compared across different timepoints. Accordingly, most nutraceutical, pharmaceutical and medical interventions have been developed for populations, with varying degree of efficacy in individuals. The most important and most impactful drugs in the history of medicine have been limited on an individual basis. The “number needed to treat” (NNT) is the number of people who need to receive the drug (or other intervention) in order for just one person to receive a benefit, can be an important number to consider. For reference, an NNT of 5 or less ( $\leq 5$ ) is probably associated with a meaningful health benefit for an individual, while an NNT of 15 or more ( $\geq 15$ ) is quite certain to be associated with, at most, a small net health benefit (Chong, et al., 2006). The NNT for the most successful drugs in history is quite high. For simvastatin, the NNT is approximately 81, which is a staggeringly high number (“Design and baseline” 1993) (“Randomized trial” 1994). Precision medicine and “N-of-1 studies” may provide an opportunity to significantly increase the efficacy of certain nutraceuticals, pharmaceuticals, and other medical interventions.

In the context of laboratory evaluation and the evaluation of certain biochemicals and laboratory measurements, the concept of the “N-of-1 study” stipulates that rather than using population-based cut-points for laboratory values and applying them to individuals, we should use an individual as their own control over time. If we are able to monitor a large suite of biochemicals and laboratory measurements in an individual over time, this will establish their own baseline, and any significant deviation from their own baseline may signal the need for further evaluation and testing by the study subject’s health care provider. This concept leads to the approach of longitudinal monitoring and surveillance over time.

Fortunately, the concept of individualized, or “precision medicine” has been gaining traction even at the level of the United States (U.S.) federal government. The Precision Medicine Initiative (PMI) was unveiled at the State of the Union Address on January 30, 2015 and had an initial investment of \$215M from the 2016 federal budget. The distilled goal of the program is “to accelerate biomedical discoveries

and provide clinicians with new tools, knowledge, and therapies to select which treatments will work best for which patients.” Simply, the PMI seeks to shift the healthcare paradigm from a one-size-fits-all approach to one which individualizes treatment plans based on individual differences in genetics, lifestyle, and environment. The original language of the initiative specifically mentions metabolomics and the microbiome, signaling the acceptance and promotion of cutting-edge health technology and research, beyond what is currently considered standard of care. Success in this area exists, most recognizably in the field of oncology, but the next steps into this frontier require the translation and broadening of current concepts to include more patients and every field of medicine. To do this, public and private collaboration will be required to leverage advances in genomics, big data, and health information technology, specifically regarding health data portability, for collaboration between patients and multidisciplinary healthcare teams. The PMI calls on millions of Americans to contribute health data to “catalyze a new era of data-based and more precise medical treatment.” Participants will have granular control of the privacy of the data they share and may withdraw consent for any component at any time, however the goal will be the creation of secure, trustworthy platforms which will engender confidence in sharing deidentified data on a longitudinal, ongoing basis, allowing physician scientists to collect and analyze that data over the course of millions of lifetimes. The PMI’s All of US research program is already the largest longitudinal study in the history of the United States.

The initial objectives of the PMI focused on strengthening existing areas of success, while broadening federal support and soliciting private support for both existing and new initiatives, with definitive commitment to patient engagement, privacy, and data security. The language of the PMI discusses the creation of a “cancer knowledge network” via funding to the National Cancer Institute for the design and testing of tailored treatments for cancer based on the genetics of patients and specific cancers. Next, the initiative calls for multi-departmental collaboration on the creation of a voluntary national research project via the National Institutes of Health, The Department of Health and Human Services, The Department of Veterans Affairs, The Department of Defense, and other relevant stakeholders, with the goal of enrolling over a million diverse individuals. Through this project, participants will contribute a wide variety of data sources “including medical records; profiles of the patient’s genes, metabolites (chemical makeup), and microorganisms in and on the body; environmental and lifestyle data; patient-generated information; and personal device and sensor data.” Radiology studies are included in this complete digital health profile, as well, as is all other available historical data, and all new data collected via the participating programs. To date, radiology studies have played a key role in the phenotyping that goes hand-in-hand with advanced genomics exploration. The amount of information in a single individual’s digital health profile can be massive, and for that reason, the big data component of the PMI is critical to the initiative’s success. As to privacy and data security, the PMI definitively commits to soliciting input from federal, public, and private entities to identify and address legal and technical issues surrounding privacy and data security, while the FDA will focus on “regulatory modernization” with specific attention to genetic testing. Lastly, the PMI emphasizes the importance of forging strong public-private partnerships for infrastructure development and patient enrollment, with attention to patient engagement and empowerment throughout each individual’s experience over their lifetimes.

Accordingly, the objective of the Puer study is to assess the impact of longitudinal, comprehensive evaluation based on certain currently available modalities in a large, unselected population of individuals.

If our study demonstrates that comprehensive baseline and longitudinal assessment employing these various modalities identifies previously unknown deviations from a study subject’s baseline, this could inform lifestyle changes and other potential interventions to maintain a healthier self. Longitudinal testing at frequent intervals, such as every 6 months, is critical, as metabolomic and proteomic changes

occur on the order of hours and days, and diseases such as pancreatic cancer can progress rapidly within a 4 to 6 month interval.

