### 2.2. Main Endpoints:

- The number of new deviations from a study subject's baseline profile 12 months after enrollment that were previously not known at time of enrollment
- The number of new deviations not known at the time of enrollment, at the following timepoints after enrollment:
  - 6 months after enrollment
  - 18 months after enrollment
  - 24 months after enrollment
- The number of new deviations identified by each employed modality

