#### 3.1. Study Schema

**Figure 1. Overall Study Schema.** The Baseline Visit includes a Medical history and physical examination (PE) Genomic Analysis, Biochemical/”Omics” Analysis and Non-Invasive Imaging. Subsequent visits at 6 months, 12 months, 18 months, 24 months and 36 months include slightly modified and targeted Medical history and PE, Biochemical/”Omics” Analysis and Non-Invasive Imaging, based on prior findings. Functional Assessments and Wearables and Quantified Self Assessments are included at the 6 months, 12 months, 18 months, 24 months and 36 months visits as determined by the Medical history and PE at the baseline visit.

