#### **3.3.2. Methodology**

Each of the visits include a combination of Medical history and PE, biochemical and “omics” assessments, non-invasive imaging assessments and optional functional assessments and wearables and quantified self-assessments.

*Medical history and PE* The Medical history and PE consists of a comprehensive “History and Physical Examination”, administered by a trained Research Associate. The elements of the history and physical examination are recorded in the Case Report Form (CRF).

- *Pregnancy Testing*

Pregnancy testing consists of a UPT for all WOCBP. The results must be negative for the subject to be able to participate in each visit.

- *Genomic Analysis*

- Whole genome sequencing (WGS) analysis (“DNA”)

- *Biochemical and “Omics” Assessments*

Biochemical and “omics” assessments consist of the following elements, using peripheral blood samples, and potentially urine, stool or saliva samples.

- Whole genome methylation analysis (“DNA methylation”)
- Whole transcriptome sequencing from circulating mononuclear cells (mRNA and miR)
- Proteomics profiling
- Metabolomics profiling
- Conventional biomarker analysis
- Urine analysis and profiling

- *Non-Invasive Imaging Assessments*

Non-invasive imaging assessment consists of the following elements, as directed, and determined by the Medical history and PE and biochemical and “omics” assessment, as described above. Imaging will follow the schedule in the table below, with an “x” indicating all participants and an “[x]” indicating imaging needed for risk-specific participants. Any deviation from the average population may trigger a dedicated organ specific MRI. Imaging may also be done at 18-, 24- and/or 36-month visits, depending on Medical history and PE at each visit, following the schedule at 6 or 12 months.

Imaging Procedure	Baseline	6 mos	12 mos
CT of head	x		
CT Angiogram of head/neck/face/sinus/orbits	x		
MRI of brain with and without contrast	x		x
MR Angiogram of head/neck time of flight			x
MRI of brain without contrast		[x]	
CT of chest, abdomen, and pelvis - mixed A/V	x	[x]	[x]
CT of chest, abdomen, and pelvis - venous only		[x]	x
MRI of spine without contrast (cervical/thoracic/lumbar)	x		x

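### The timed deviation counts in section 2.2 pool all modalities, but imaging is fixed for everyone at only one follow-up visit, so differences between timepoints partly reflect who was imaged.

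*Protocol*

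**What the plan says.** - **Protocol 1.2 (Rationale).** "Longitudinal testing at frequent intervals, such as every 6 months, is critical". Two reasons follow: metabolomic and proteomic change over hours to days, and that "diseases such as pancreatic cancer can progress rapidly within a 4 to 6 month interval".
- **Protocol 2.2 (Main Endpoints).** The first endpoint is the 12-month count of deviations from the participant's baseline. The second is "The number of new deviations not known at the time of enrollment, at the following timepoints after enrollment", listing 6, 18 and 24 months. The third is a count for each modality, with no timepoint and no denominator.
- **Protocol 3.3.2 (Methodology).** In the imaging table an x means all participants, and a bracketed x is described as "indicating imaging needed for risk-specific participants". The table covers baseline, 6 and 12 months. For later visits: "Imaging may also be done at 18-, 24- and/or 36-month visits, depending on Medical history and PE at each visit", following the 6- or 12-month column. A finding away from the population average may also trigger an organ-specific MRI.
- **Protocol Synopsis (Study Schedule).** Imaging is marked at all six visits, with a footnote that refers to section 3.3.2 for the detail. History and examination, and biochemical/omics analysis, are also marked at all six.
- **Protocol 3.1 (Study Schema).** "Subsequent visits at 6 months, 12 months, 18 months, 24 months and 36 months include slightly modified and targeted Medical history and PE". The same sentence extends to omics and imaging, all based on prior findings.

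**The concern.** A count of new findings at successive visits shows when deviations arise only if people are looked at in the same way each time. Here one of the three key elements of the evaluation is applied to the whole cohort at one follow-up visit and to a selected group at the others. Findings that arose before month 6 in participants not imaged at month 6 would first appear at month 12 and be booked there.

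The main objective in section 2.1 concerns deviations that develop over time, so this artefact falls on a main result. The second objective, finding the modality with the highest impact, is exposed too, because a modality applied to everyone more often has more chances to find something. The study is descriptive, so no test or model would correct for this; readers will take the tabulated numbers at face value.

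**Working it through.** The protocol gives no figure to reproduce on this point. The check is a tally of the schedule and two illustrations.

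**Imaging table, section 3.3.2 (10 procedures).**

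| Visit | All participants (x) | Risk-specific ([x]) |
|---|---|---|
| Baseline | 7 | 0 |
| Month 6 | 0 | 5 |
| Month 12 | 6 | 1 |
| Months 18, 24, 36 | not fixed | not fixed |

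**Interval.** The only fixed all-participant imaging interval is baseline to month 12: nominally 12 months, or 11 to 13 with the ±1-month window (baseline has none). Against the cited 4 to 6 months, 12/6 = 2 and 12/4 = 3, so it is two to three times as long. Visits themselves are 6 months apart up to month 24: 5 to 7 months for the first gap and 4 to 8 for each of the next three.

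**Looks by modality up to month 24.** History/examination and omics are scheduled at 6, 12, 18 and 24 months, giving 4 follow-up looks. Imaging has 1 that is fixed for all, at month 12.

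**Illustration 1: imaging findings only.** Assume a constant onset rate of one unit per 6 months. A share r is imaged at month 6 and everyone at month 12. Findings persist until seen, and those imaged at month 6 have the same rate as the rest. The value of r is not in the protocol.

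- New at month 6: r
- New at month 12: 2 − r (everything since baseline, less what was already found)
- Ratio of new findings, month 12 to month 6: (2 − r)/r
- Ratio of cumulative findings: 2/r, against a true value of 2

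| r | New: month 6 | New: month 12 | Ratio, new | Ratio, cumulative |
|---|---|---|---|---|
| 10% | 0.10 | 1.90 | 19 | 20 |
| 25% | 0.25 | 1.75 | 7 | 8 |
| 50% | 0.50 | 1.50 | 3 | 4 |
| 100% | 1 | 1 | 1 | 2 |

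If those imaged at month 6 have k times the onset rate of the others, month 6 yields rk and month 12 yields 2(rk + 1 − r) − rk. The ratio of new findings is then 1 + 2(1 − r)/(rk). A higher k shrinks the distortion, but the ratio stays above 1 whenever r is below 100%.

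**Illustration 2: pooled count.** Assume history/examination and omics give 2 deviations per person per visit, full imaging gives 1 at month 12, and targeted imaging adds nothing elsewhere (the limiting case).

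- Counted per visit: 2, 3, 2, 2 at 6, 12, 18 and 24 months
- Counted cumulatively: 2, 5, 7, 9

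The cumulative series has no peak and no fall, but its month-12 step is 3 against 2 elsewhere. Either way the excess is 50% (3/2) and comes from the schedule alone.

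**The case against.** Much of the other side's case is sound.

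- **The 12-month endpoint is aligned with the schedule.** It is listed first, and baseline and month 12 are the two points with all-participant imaging. This stands: the problem lies in comparing timepoints, much less in the 12-month count on its own.
- **A reader might infer that section 1.2 and the schedule flatly contradict each other.** They do not. Six months is given as an example and is not tied to imaging, and history/examination and omics are scheduled 6-monthly up to month 24. What remains is a tension confined to imaging.
- **A reader might infer that the synopsis imaging row contradicts section 3.3.2.** Its footnote defers to that section, so the row needs aligning but is not a rival schedule.
- **A reader might infer that the count must peak at month 12 and fall at month 18.** That requires per-visit counting. Section 2.2 takes enrollment as the reference, which suggests cumulative counts; these show a larger step and no fall.
- **A reader might infer that nobody outside a flagged group is imaged at 18 or 24 months.** The text leaves the number open, since either the 6- or the 12-month column may be followed.
- **A reader might infer that the gap between months 24 and 36 distorts the timed counts.** It cannot, because they end at month 24. Month 36 enters only the exploratory counts of unscheduled care, and at most the untimed per-modality count.
- **Modality is already separated, and tabulation belongs in an analysis plan.** The per-modality endpoint has no timepoint or denominator, and the timed endpoints are pooled by their protocol definition. An unseen analysis plan may tabulate further, but the definition and the uneven schedule both sit in the protocol.
- **History/examination and omics are not a guaranteed uniform series.** Section 3.1 describes them as targeted at follow-up. This stands and limits the fix.

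**Conclusion.** The point holds for the imaging contribution to the counts at 6, 12, 18 and 24 months, and for the comparison of modalities. Differences between timepoints in the pooled count cannot be read as the timing of deviations, because imaging covers everyone at month 12 and an unspecified, selected group at the other three.

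The size cannot be derived from the protocol, which does not say how many participants will be imaged at those visits. For imaging alone, the month-12 to month-6 ratio of new findings runs from 19 down to 3 for assumed shares of 10% to 50%, where the true ratio is 1. In the pooled count the effect is diluted by the other modalities. These figures assume constant onset, findings that persist until seen, and no higher onset rate in those selected.

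Nothing here shows that the first-listed 12-month count is unusable or that the visit schedule is wrong. The issue should be corrected, at low cost, and it does not invalidate the study.

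**What to change.** 1. In section 2.2, report each timed count by modality and visit, with the number of participants actually assessed by that modality at that visit as denominator. State whether counts are per visit or cumulative from enrollment.
2. Identify month 12 as the only follow-up timepoint with all-participant imaging. Label imaging counts at 6, 18 and 24 months as coming from a selected subset.
3. Draw time-course statements only from assessments confirmed to be done in the same way for everyone at each visit. Given section 3.1, the sponsor must first confirm which parts of history/examination and omics meet this.
4. Present the per-modality comparison with the number of looks and the number assessed for each modality.
5. Reconcile the 6-month statement in section 1.2 and the synopsis imaging row with the section 3.3.2 table. Which imaging schedule is right is a clinical matter and is not addressed here.

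The cost is endpoint and rationale wording and slightly more tabulation of data already collected. No visit or scan is added. The downside is a narrower headline time course, with "non-invasive imaging" findings shown beside it instead of pooled into it.
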